Topical 20% benzocaine (Ultracare Oral Anesthetic Gel, Ultradent, South Jordan, Utah will be used on the intraoral tissue at site of injection for 5 minutes, and then the tissue will be injected. Patients will be informed when the tissue is pierced and again when the local anesthesia is being administered. Participants receiving an IANB will be injected with 0.85mL (50% volume of a 1.7mL carpule) of 2% lidocaine with 1:100,000 epinephrine approximately. Patients receiving a buccal infiltration in the maxilla will receive 0.425mL (25% volume of a 1.7mL carpule) of solution over 15 seconds. The operator will aspirate prior to administration of local anesthetic solution in all cases; a positive aspiration will require redirection of the needle or repositioning before injection. Patients will be asked to rate their pain related to administration of solution (the second prompt) once the injection is finished. Patients will be observed during injection and assessed by the operator using the Faces, Legs, Arms, Crying Consolability (FLACC) scale. Immediately after local anesthesia, patients will be asked to rate the pain of injection of solution using the Wong-Baker FACES Pain Scale. These scales were selected because they are approved for use by the AAPD for children over the age of 3 and have been used successfully in previous studies investigating pain perception in child subjects.^{7,14}

After administration of local anesthetic solution, the onset time of soft tissue anesthesia will be measured by using a periodontal probe in the sulcus of the anesthetized tooth or a single tooth in the anesthetized quadrant. This probing will be initiated 15 seconds after initial injection of anesthetic solution and will be repeated at 15 second intervals until local anesthesia is achieved. After each probing attempt, patients will be asked if they felt a "pinch". Once the patient answers "no," the time of onset, in number of seconds to achieve anesthesia from injection to a "no" answer, will be recorded.

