In the event of a missed block, the patient will be excluded from the study. The second attempt for local anesthesia will be made with the effort to achieve profound local anesthesia, and the technique and type of local anesthesia will not be limited to the techniques or anesthetic solutions described in this study. Local anesthesia techniques and solutions used in the event of a missed block will be within the scope of practice for a pediatric dental patient, however, this event will be considered a potential confounding variable in our research study.

A second protected Excel spreadsheet will be used to record patient's scores for the Wong-Baker FACES Pain Scale, the FLACC scale and the time of onset of local anesthesia. This spreadsheet will also include the patient's name, MRN number, the side of the mouth that was treated, the location of the injection, the injection technique, and the date of each visit. This spreadsheet will be available to the operator in order to record the clinical outcomes related to each encounter; it will not affect the double-blind nature

GEISINGE IRB NUMBER: 2019-0408 IRB Approved: 12/12/2019

of this study, as the operator will not know which local anesthetic preparation was used during each encounter.

After the first day of treatment, a "wash out" period of at least 1 week will be required before the patient can return for treatment on the other side of the mouth, and the administration of the alternate type of local anesthetic solution. Wash out periods have been used in many similar studies to minimize bias.^{1,7,11}

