5.2.3 EXCLUSION CRITERIA

- 1. Patients with allergy to local anesthetic
- 2. Patients who are pregnant or nursing
- 3. Patients with cardiac concerns or contraindications to epinephrine
- 4. Patients unable to undergo dental treatment in the clinic for behavior or medical reasons
- 5. Patients requiring anxiolysis, sedation, or general anesthesia
- 6. Patients unable to keep dental appointments or return for dental appointments
- 7. Patients who do not meet inclusion criteria
- 8. Patients who experience a missed block (IANB) during injection

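### Onset probing has no maximum time, and an undefined missed block removes a randomised child from the study, so onset failures, and on the natural reading the pain pair, are lost

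*Combined protocol and SAP*

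**What the plan says.** Section 5.1 starts probing 15 seconds after injection, and it "will be repeated at 15 second intervals until local anesthesia is achieved". The endpoint is the time "in number of seconds to achieve anesthesia from injection to a" negative answer from the child. No value is given for a child who never gives that answer, and no time or number of probes ends the attempt.

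Pain comes earlier. FLACC is scored by observation during the injection, and for the self-report: "Immediately after local anesthesia, patients will be asked to rate the pain of injection of solution using the Wong-Baker FACES Pain Scale".

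On failure, section 5.1 says: "In the event of a missed block, the patient will be excluded from the study". It continues: "The second attempt for local anesthesia will be made with the effort to achieve profound local anesthesia", with technique and solution left open, and adds that "this event will be considered a potential confounding variable in our research study". Section 5.2.3 item 8 lists as an exclusion: "Patients who experience a missed block (IANB) during injection". Maxillary cases are treated by infiltration; such a child "will receive 0.425mL (25% volume of a 1.7mL carpule) of solution over 15 seconds".

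Section 5.5.1 plans paired t-tests, or repeated-measures ANOVA if covariates are identified. It defines no analysis set and no method for an onset that was not reached. Section 5.5.2 plans 55 children, with 11 allowed for attrition, and does not mention missed blocks.

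**The concern.** Probing until success and declaring a miss cannot both operate unless something says when one gives way to the other. Three things are at stake.

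- **Burden.** Children from age 4, treated without sedation or anxiolysis, are probed at a fixed rate with no written stopping point. The stop is left to judgement and may differ between children, or between one child's two visits.
- **Onset (Aim 3).** Failing to become numb is the worst value the onset outcome can take. The plan removes the child for it, after the coin flip has set the order of solutions. If buffering changes how often injections fail, dropping the failures changes the onset comparison.
- **Pain (the primary aim in section 3).** The pain scores at the failed visit were taken before anyone could know of the failure. A miss at the first visit ends participation before the second. After a miss at the second visit, both pain scores exist and nothing says they are kept.

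**Working it through.** **1. The sections side by side.**

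| Question | Mandibular block | Maxillary infiltration |
|---|---|---|
| When does probing stop without success? | When the block is judged missed; no criterion given | Not stated |
| Does the child stay in? | No (5.1; 5.2.3 item 8) | Not clearly stated: item 8 names the block only, while the second-attempt sentence in 5.1 could be read more widely |
| What onset value is recorded? | None | None |
| Is pain already scored? | Yes | Yes |
| Are the pain scores analysed? | Not stated; exclusion from the study suggests not | Not stated |

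**2. Probing rate (5.1).** One probe per 15 s gives 60/15 = 4 per minute. That is 300/15 = 20 by 5 minutes and 600/15 = 40 by 10 minutes. These illustrate the schedule; they are not expected exposures.

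**3. The plan's own sample size (5.5.2).** Inputs: d = 0.50, 90% power, 20% attrition. Alpha is not stated, so I assume two-sided 0.05. With the noncentral t distribution (df = n − 1, noncentrality d√n), the smallest n is 44, with power 0.900. Then 44/(1 − 0.20) = 55. The plan's figures reproduce.

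**4. Pairs lost to missed blocks.** The documents give neither a miss rate per injection (q) nor the share of children treated in the mandible (m), so both are assumed. A miss at either visit costs the pair. With visits independent, L = 1 − (1 − q)², and the expected loss is 55 × m × L.

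| q | L | m = 0.25 | m = 0.5 | m = 0.75 | m = 1 |
|---|---|---|---|---|---|
| 2% | 0.0396 | 0.5 | 1.1 | 1.6 | 2.2 |
| 5% | 0.0975 | 1.3 | 2.7 | 4.0 | 5.4 |
| 10% | 0.19 | 2.6 | 5.2 | 7.8 | 10.5 |

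The allowance for all causes is 55 − 44 = 11. Every entry is below it, and only the 10% row with m of 0.75 or 1 uses most of it.

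**5. Power if these losses come on top of all 11.** Remaining pairs are 44 × (1 − m × L).

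- q = 5%, m = 0.5: 44 × (1 − 0.04875) = 41.9, about 42 pairs, power 0.886.
- q = 10%, m = 0.5: 44 × (1 − 0.095) = 39.8, about 40 pairs, power 0.869.
- q = 10%, m = 1: 44 × (1 − 0.19) = 35.6, about 36 pairs, power 0.831.
- Extreme, q = 20%, m = 1: 44 × (1 − 0.36) = 28.2, about 28 pairs, power 0.723. Nothing in the documents points to this; Aims 2 and 4 expect both techniques.

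**6. Onset, as illustration only.** A simulation assumed lognormal onset (log-SD 0.8), within-child correlation 0.5, a 600 s cap, and failure meaning onset beyond the cap.

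| Assumed failure, buffered / conventional | Pairs dropped | Mean difference, failures excluded | Mean difference, all kept and capped |
|---|---|---|---|
| 5% / 15% | 17% | 76 s | 96 s |
| 10% / 10% | 17% | about 0 s | about 0 s |

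Exclusion matters for the contrast when failure differs by solution. In the equal-failure case simulated, it did not.

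**The case against.** The strongest reply is that a clinician knows a missed block, the operator is blinded, and an attending dentist oversees treatment. Much of this stands. For a mandibular block the exclusion rule is itself an exit from probing, section 5.4.1 puts visits at 30 to 90 minutes, and section 5.1 mentions families choosing to leave. A reader might infer that children will be probed endlessly; the documents make that unlikely. What is missing is the trigger. Blinding prevents a decision based on known allocation, but it does not prevent selection on an outcome that the solution may affect.

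Item 8 speaks of a miss during injection, which may mean that the needle missed the nerve, not that onset was slow. That reading is open and would weaken the link to the onset outcome. But probing is the only check of numbness the plan describes, and no criterion separates a technical miss from slow onset.

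A reader might also infer that the plan deletes pain scores already recorded. It does not say so. It says that the child is excluded and is silent on the scores; loss is the natural reading, not a stated rule.

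There is a real argument for leaving out first-visit misses: an unrestricted rescue injection could affect the child's pain rating at the second visit. It does not reach a miss at the second visit, when both pain scores precede any rescue at that visit. It is better met by a sensitivity analysis than by exclusion.

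Finally, it is tempting to conclude that the onset result will be biased in a known direction, or that the trial is underpowered. The documents give no failure rates, so neither follows. Nor is a bias claimed for Aim 4, which is non-randomised and confounded by arch and volume (0.85 mL against 0.425 mL) whatever the failure rule.

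**Conclusion.** The point holds as a gap in the endpoint definition and the analysis set. Probing has no cap, a missed block has no definition, a failed infiltration is not clearly covered, and a randomised child is removed on an event tied to the onset outcome. The planned t-tests and ANOVA have no place for an onset that was never reached.

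The effect on onset cannot be sized or signed from the documents. The effect on the primary pain analysis is a loss of pairs, on the natural reading of exclusion. At assumed miss rates up to 10% that loss lies within the allowance of 11 if little else is lost in the heaviest scenarios. If it falls wholly on top of the allowance, power goes from 90% to about 87% (half mandibular) or 83% (all mandibular). These figures rest on assumed miss rates, an assumed mandibular share, independence between visits and two-sided alpha of 0.05. The sample-size calculation itself is correct. This is a cheap improvement.

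**What to change.** - **Section 5.1, probing.** Set one maximum probing time, the value for the sponsor to choose, the same for both solutions and both techniques. When it is reached, stop probing, record that the child was not anaesthetised by the cap, and give usual-care anaesthesia.
- **Section 5.1, missed-block paragraph, and 5.2.3 item 8.** State that a failed injection of either technique does not exclude the child. The child returns for the second visit, and the pain scores stay in the paired pain analysis.
- **Section 5.5.1, pain.** Add a sensitivity analysis omitting children who had a rescue injection at the first visit.
- **Section 5.5.1, onset.** Keep failures as later than the cap. Use a simple paired rank test in which a failure ranks slower than every observed time and a pair with two failures is a tie. More elaborate methods for censored pairs are optional. Add a sensitivity analysis limited to children with successful injections at both visits, and report failure counts by solution and technique.

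The cost is a few sentences. No extra patients, staff or procedures are needed, and the child already needs treatment on the other side of the mouth. There are three downsides. Onset beyond the cap is known only as later than the cap. Technical misses are mixed with slow onset in the main onset analysis. A first-visit rescue injection may affect the second-visit pain rating. The sensitivity analyses address the last two.

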This project's primary aim is to evaluate pain perception in buffered vs non-buffered local anesthetic administration in children undergoing routine dental treatment. The secondary aim is to evaluate if the buffered solution results in a faster onset of local anesthesia compared to conventional solution. Through a well-designed study, we hope to contribute to the profession's understanding of advanced local anesthesia techniques in children.

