4. HYPOTHESIS AND SPECIFIC AIMS

4.1 HYPOTHESIS:

- 4.1.1 Null Hypothesis: There will be no significant difference between buffered local anesthesia vs conventional anesthesia in pain reduction.
- 4.1.2 Null Hypothesis: There will be no significant reduction in time between buffered local anesthesia vs conventional anesthesia achieving soft tissue anesthesia.
- 4.1.3 Hypothesis: There will be a statistically significant reduction in pain on intraoral administration of buffered 2% lidocaine with 1:100,000 epinephrine compared to non-buffered 2% lidocaine w/1:100,000 epinephrine in children.
- 4.1.4 Hypothesis: Buffered 2% lidocaine with 1:100,000 epinephrine will have a statically significant faster onset of soft tissue anesthesia compared to non-buffered 2% lidocaine w/1:100,000 epinephrine in children

4.2 SPECIFIC AIM 1:

To determine if buffering 2% lidocaine with 1:100,000 epinephrine reduces discomfort experienced on injection compared to non-buffered solution in children with a split mouth design

4.3 SPECIFIC AIM 2:

To compare infiltration vs inferior alveolar nerve block (IANB) in experience of pain reduction with buffered 2% lidocaine with 1:100,000 epinephrine on injection in children among different groups; patients will either receive two or more infiltrations or two or more IANBs.

4.4 SPECIFIC AIM 3:

To determine if buffering 2% lidocaine with 1:100,000 epinephrine reduces onset time of local anesthesia compared to non-buffered solution in children

4.5 SPECIFIC AIM 4:

[figure not shown]
To compare onset time of local anesthetic via infiltration versus IANB using buffered 2% lidocaine with 1:100,000 epinephrine in children

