During the appointment requiring the buffered local anesthesia solution, the attending will prepare 1:10 dilution of sodium bicarbonate to local anesthesia. A 1.7mL vial of commercially available 2% lidocaine hydrochloric acid with 1:100,000 epinephrine (Lignospan standard, Septodont Lancaster, Pennsylvania (PA) will be used. The cartridge of lidocaine and the bottle of sodium bicarbonate will be wiped with an alcohol pad. 0.17mL of 8.4 percent sodium bicarbonate will be added into the local anesthesia cartridge to make the final preparation. The pH of traditional 2% lidocaine with 1:100,000 epinephrine is typically acidic to prolong shelf life; the pH is approximately 4.5.8 The buffered solution will be tested using a pH tester (Water Quality Test Meter Pancellent TDS PH EC Temperature 4 in 1 Kit, Pancellent) to evaluate the pH range of this preparation, and to verify a value above 5.5.

The attending will bring the cartridge of anesthetic to the operatory and load the syringe. The operator and patient will remain blinded to the type of local anesthesia that is used. For this study, if the patient requires treatment of the lower posterior teeth, a IANB will be the injection technique of choice. If the patient requires treatment in the posterior maxilla, an infiltration will be the injection technique of choice. After a period of no less than one week, the patient will return for a second visit. At the second visit, the solution of local anesthesia will be alternated, and the opposite side of the mouth will be treated.

Prior to initiation of treatment, patients will rate their pain using the Wong-Baker FACES Pain Scale in order to establish a baseline and to help eliminate confounding variables. Also before treatment, a tooth that will be anesthetized will be probed with a periodontal probe to establish a baseline perception of this sensation without local anesthesia. Upon probing without local anesthesia, the patient will ask if they feel a "pinch," in order to

establish this baseline. When asked if they feel a pinch, patients will respond with a "yes" or "no" answer, which will be recorded.

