5.2.2 INCLUSION CRITERIA

- 1. Patients requiring restorative or surgical dental treatment on two or more occasions on opposite sides of the mouth; either both maxillary or both mandibular quadrant/sextant involving comparable teeth/areas
- 2. Patients able to undergo dental treatment in the dental clinic without general anesthesia, sedation, or anxiolysis
- 3. Patients 4-17 years of age
- 4. Patients classified as ASA I or ASA II
- 5. Patients of parents who can read, write and give consent in English

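### Onset probing stops at the first unconfirmed 'no'; if stray answers are equally likely with both solutions, this on average pulls the Aim 3 onset difference toward zero

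*Combined protocol and SAP*

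**What the plan says.** Section 5.1 starts probing 15 s after injection, and probing "will be repeated at 15 second intervals until local anesthesia is achieved". After each probe the child is asked about a pinch. The rule that ends the measurement begins "Once the patient answers 'no,' the time of onset", and onset is the number of seconds from injection to that answer. The section gives no repeat probe, control-site probe, second observer or time limit.

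Two other provisions come near this point:
- **Baseline probe (5.1).** Before anesthesia, "patients will respond with a 'yes' or 'no' answer, which will be recorded". No consequence is attached to either answer.
- **Missed block (5.1 and exclusion criterion 8 in 5.2.3).** The child is excluded, but the rule is not tied to the probe answers.

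Eligibility (5.2.2) is "Patients 4-17 years of age". Section 3 makes onset secondary: "The secondary aim is to evaluate if the buffered solution results in a faster onset of local anesthesia compared to conventional solution". Aim 3 (4.4) asks whether buffering "reduces onset time of local anesthesia compared to non-buffered solution in children". On blinding, 5.1 says "The operator and patient will remain blinded to the type of local anesthesia that is used".

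**The concern.** The stopping rule treats the two kinds of wrong answer differently. A mistaken 'yes' after true onset is put right at the next probe and costs one interval. A mistaken 'no' before true onset is final. The recorded time for that visit is then too short, and because probing has stopped, the data hold nothing from which the error could be found or corrected in the analysis. A clear 'yes' at the baseline probe does not prevent it.

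The longer the true onset, the more probes precede it and the more often a stray 'no' can end the measurement. The slower solution is therefore cut short more often when the chance per probe is the same for both. At stake is the trial's ability to show the faster onset stated in hypothesis 4.1.4. Some children who can still feel the probe would also be recorded as anesthetized.

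**Working it through.** **The plan's own figure.** Section 5.5.2 gives 44 evaluable patients for 90% power at d = 0.50. A paired t-test at two-sided 0.05 (alpha and sidedness are not stated, so this is assumed) needs n = 44, with power 0.900; 44 / (1 − 0.20) = 55. The figure reproduces. The plan does not tie d = 0.50 to pain or to onset.

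**Inputs.** From 5.1: the 15 s interval and the first-'no' rule. Assumed, because the documents give neither: true onset 120 s (conventional) and 90 s (buffered), so the first truly numb probe is k = 8 or k = 6; stray-'no' probability p = 0.02, 0.05 or 0.10 at each earlier probe, the same for both solutions; always 'no' from true onset onward.

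**One 'no' ends probing.** Mean recorded onset = 15 × (1 − (1 − p)^k) / p. For p = 0.05:
- conventional: 300 × (1 − 0.95^8) = 300 × (1 − 0.6634) = 101.0 s
- buffered: 300 × (1 − 0.95^6) = 300 × (1 − 0.7351) = 79.5 s
- difference: 21.5 s against a true 30 s

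The same difference can be written 15 × (0.95^6 + 0.95^7) = 15 × (0.7351 + 0.6983) = 21.5 s. Each 15 s step of the true difference counts only with the probability that the child has not already stopped. With equal p above zero, the expected difference is therefore always below the true one. If the two onsets are equal, it is zero.

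The probability of an early stop is 1 − (1 − p)^(k−1): for the slower solution 13%, 30% and 52%; for the faster 10%, 23% and 41%.

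**Two consecutive 'no' answers, onset timed at the first.** Calculated by exact recursion, first with independent errors, then with an assumed 80% chance that a stray 'no' is repeated at the next probe.

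| p | One 'no': difference | Two 'no', independent | Two 'no', 80% repeated |
|---|---|---|---|
| 0.02 | 26.3 s | 29.9 s | about 27 s |
| 0.05 | 21.5 s | 29.5 s | about 23 s |
| 0.10 | 15.1 s | 28.3 s | about 18 s |

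Early stops with the slower solution under the two-'no' rule are 2%, 6% and 14% with independent errors, and 11%, 25% and 45% with 80% repetition.

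**Longer onsets.** Under the one-'no' rule with p = 0.02, 0.05 and 0.10, true onsets of 180 and 120 s leave 49.5, 36.9 and 22.2 s of 60 s (83%, 62%, 37%). True onsets of 300 and 180 s leave 73%, 45% and 20% of 120 s.

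**Power for onset.** Simulation of 4,000 trials of 44 pairs, with true d = 0.50 for onset, mean onsets of 120 and 90 s, and a between-child SD of 20 s (all assumed). Without stray answers power is about 90%. Under the one-'no' rule it is about 73%, 52% and 31%. Under the two-'no' rule with independent errors it is about 89.5%, 87% and 82%.

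**Single pairs.** At 180 and 120 s with p = 0.05, about 60% of pairs are affected. Of these, about 65% show a smaller difference and about 34% a larger one.

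**Unequal rates.** At 180 and 120 s, p = 0.02 conventional and 0.05 buffered gives 161.5 − 101.0 = 60.5 s against a true 60 s. With 0 and 0.05 it is 180 − 101.0 = 79.0 s.

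**The case against.** A reader might infer four stronger things, and the documents support none of them.

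- **That any stray 'no' narrows the difference.** One at the conventional visit does; one at the buffered visit widens that child's difference. The shrinkage is an average, and it needs equal rates per probe. Blinding makes equal rates plausible but does not establish them, and unequal rates can cancel or reverse the effect.
- **That Aim 4 shrinks as well.** Blinding covers the solution, not the technique. Section 5.1 fixes technique by arch, inclusion criterion 1 pairs visits within one arch, and Aim 2 describes technique as compared among different groups. Stray-answer rates could differ with age mix and site, so no direction follows.
- **That a second 'no' restores nearly the whole difference.** That holds only for independent errors. A child who has learned that 'no' ends the probing would tend to repeat it. The documents do not say that this happens, but if it does, much less is recovered.
- **That the trial risks a false claim of faster onset.** With equal rates and no true difference in onset, the rule creates no bias. The loss is in sensitivity.

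It is also fair to say that the size cannot be derived from the documents: the illustrations run from slight to severe, and nothing favors either end. The baseline probe is a partial check that the child feels and reports a pinch. Onset is a secondary aim. All of this limits the point. It does not answer the fact that a false 'no' is final and leaves no trace.

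**Conclusion.** The point holds in a limited form. The onset measurement rests on one unconfirmed answer from a child who may be 4 years old. An error in one direction is re-tested; an error in the other is permanent and undetectable. On average this biases the Aim 3 difference toward zero, provided stray 'no' answers are equally likely per probe with both solutions.

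Under the assumed 120 and 90 s with 2% to 10% stray answers, between about 26 and 15 s of a true 30 s remains. These figures show how the rule behaves; they do not estimate what will happen in this trial. Requiring a second 'no' improved matters in every case calculated, but the repair is close to complete only when errors are independent. The primary pain comparison is not affected. It is a worthwhile, inexpensive improvement to a secondary endpoint.

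**What to change.** Amend the onset paragraph of section 5.1 so that probing ends after two consecutive 'no' answers 15 s apart, onset is recorded as the time of the first of the two, and a 'no' followed by a 'yes' counts as not yet numb.

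The cost is one sentence in the protocol, one extra probe and about 15 s per visit. There are two drawbacks. A stray 'yes' after true onset can delay the recorded time by an interval or two. The rule also reduces, but does not remove, error from a child who keeps saying 'no' to end the probing.

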On the day of the procedure, the side of the mouth that is treated first will be based on the patient's chief complaint. If the patient does not have a chief complaint, the side of the mouth that is treated first will be the side of the mouth with more significant dental caries. The attending pediatric dentist will flip a coin to determine if the patient will receive the buffered or conventional local anesthetic solution during the first visit, with the "heads" side being assigned to the buffered solution, and the "tails" side assigned to the non-buffered solution. At the patient's second visit, the alternative local anesthetic solution will be used, and the other side of the mouth will be treated.

IRB NUMBER: 2019-0408 IRB Approved: 12/12/2019

[figure not shown]
The attending pediatric dentist will have access to a protected Excel spreadsheet containing information related to each patient including: patient name, medical record number (MRN), the patient's number assignment (as discussed above), date of the first and second visit, which local anesthetic solution was administered at each visit, the local anesthesia technique used (infiltration vs IANB), which arch (maxilla vs mandible) was treated, and which side of the mouth was treated. This document will be locked and the operator will not have access to this spreadsheet in order to preserve the double-blind nature of this study.

Vasoconstrictors, like epinephrine, become unstable with an increase in pH⁹. Local anesthetic solutions with a vasoconstrictor are traditionally prepared as an acidic solution to extend shelf life⁹. Buffering our local anesthesia containing epinephrine will reduce the stability of solution from approximately 8-12 months to a shelf life of only seven days¹³. Although the solution has been said to be stable for a week, to ensure stability of the solution, and control for confounding variables, the buffered solutions will be mixed immediately before administering the solution. Other study designs have used this approach to mix the solution immediately before administration^{1,9}.

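### A missed nerve block, seen only after the coin flip and pain scoring, excludes the child: usable pain pairs are lost and IANB onset is compared only where blocks worked

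*Combined protocol and SAP*

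**What the plan says.** Section 5.1 has the solution assigned on the day of the procedure: "The attending pediatric dentist will flip a coin to determine if the patient will receive the buffered or conventional local anesthetic solution". FLACC is scored by the operator while the injection is given, and then "Immediately after local anesthesia, patients will be asked to rate the pain of injection of solution using the Wong-Baker FACES Pain Scale". Probing for onset follows. It is "repeated at 15 second intervals until local anesthesia is achieved", and what is recorded is "the time of onset, in number of seconds to achieve anesthesia from injection to a" negative answer from the child. No upper limit on probing is stated.

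On failure, 5.1 says "In the event of a missed block, the patient will be excluded from the study" and adds that "this event will be considered a potential confounding variable in our research study". Section 5.2.3 lists the same event as exclusion criterion 8: "Patients who experience a missed block (IANB) during injection". It names the IANB only. Section 5.1 also says that "A second protected Excel spreadsheet will be used to record patient's scores for the Wong-Baker FACES Pain Scale, the FLACC scale" and the onset time.

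Section 5.5.1 specifies paired t-tests, or repeated-measures ANOVA if covariates are identified. It names no analysis set, gives no rule for scores recorded before an exclusion, and gives no rule for onset that is not reached. Section 5.5.2 plans 55 children, 90% power at d = 0.50 and 20% attrition (11 children), leaving 44 pairs. It does not say whether missed blocks count within that 20%.

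**The concern.** Criterion 8 cannot be applied at screening. It depends on a result of the randomised treatment, seen after the primary-aim scores have been taken.

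- **Pain (primary aim, Aim 1).** The outcome is the pain of injecting the solution. Whether the tooth later goes numb does not make that rating missing or invalid. A child whose block misses at visit 2 has a complete pain pair, and the rule as written takes it out of the paired analysis.
- **Onset (Aim 3).** Among IANB children, the comparison is confined to those whose blocks worked, which is a selection made after the coin flip. If the solution influences block success, the mean difference in seconds among the remaining pairs need not equal the effect in all children injected. No report of misses by solution is planned, so a reader could not judge this.
- **Infiltration.** A failed infiltration also yields no onset time but falls under no rule. The two techniques compared in Aims 2 and 4 are therefore handled unevenly. Those comparisons are not randomised in any case, because the arch treated sets the technique.

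**Working it through.** **1. Order of events in 5.1.** Coin flip; injection with FLACC; FACES immediately afterwards; probing every 15 seconds; missed block recognised; child excluded. Criterion 8 places the miss at the time of injection, but probing is the only check of anesthesia described. Exclusion therefore follows both pain scores.

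**2. The plan's own figure.** Paired t-test, noncentral t with n − 1 degrees of freedom and noncentrality d√n. Alpha and sidedness are not stated; 5% two-sided is assumed. With d = 0.5 and n = 44, the noncentrality is 0.5 × √44 = 3.317 and power is 0.900. Inflation for attrition: 44 / (1 − 0.20) = 55. The plan's 44, 55 and 90% all reproduce.

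**3. Children and pairs lost.** The documents give neither the miss rate nor the IANB share. Assumptions: half of 55 children receive IANB (27.5), and the miss rate m per injection is 5% to 20%, independent between visits.

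- Excluded under the rule: 27.5 × [1 − (1 − m)²] = 2.7 to 9.9
- Missed at visit 1: 27.5 × m = 1.4 to 5.5
- Missed only at visit 2, so a complete pain pair is lost: 27.5 × m × (1 − m) = 1.3 to 4.4

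**4. Power for pain at d = 0.5.** The pairs-kept rows assume that children with a visit-1 miss do not continue, so only visit-2 misses are recovered.

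| Case | Pairs, m = 5% | Power | Pairs, m = 20% | Power |
|---|---|---|---|---|
| Rule, misses on top of 20% attrition | 0.8 × (55 − 2.68) = 41.9 | 0.88 | 0.8 × (55 − 9.9) = 36.1 | 0.83 |
| Visit-2 pairs kept, same attrition | 0.8 × (55 − 1.375) = 42.9 | 0.89 | 0.8 × (55 − 5.5) = 39.6 | 0.87 |
| Rule, misses the only loss | 52.3 | 0.94 | 45.1 | 0.91 |
| Visit-2 pairs kept, misses the only loss | 53.6 | 0.95 | 49.5 | 0.93 |

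With misses on top of attrition, keeping the pairs gains 0.8 points of power at m = 5% (0.8845 to 0.8923) and 3.4 points at m = 20% (0.8315 to 0.8659).

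**5. Other IANB shares, misses on top of attrition.** At 25%: 0.87–0.89 under the rule against 0.88–0.90 with pairs kept. At 75%: 0.78–0.88 against 0.85–0.89.

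**6. Onset.** No figure is derived. The direction and size of any bias depend on how often blocks miss with each solution, and on whether a miss is a slow onset or a misplaced needle. The documents give neither. If misses are unrelated to the solution, the exclusion causes no bias.

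**The case against.** The strongest case against has four parts.

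- **The primary outcome is barely touched.** At half IANB, the 2.7–9.9 exclusions fit within the allowance of 11, and 5.5.2 does not say that missed blocks lie outside it. If they are the only loss, power stays above 90% either way. This stands, and it limits the power argument to the case where misses add to other attrition.
- **Excluding missed blocks from the pain analysis is defensible.** A child who had a failed block and a second attempt at visit 1 may rate visit 2 differently. This stands as a reason to report such an analysis. It does not support making it the only one, and it does not apply to a miss at visit 2, where both scores precede the failure.
- **A rank test gives no estimate in seconds.** This is right, so it should supplement the paired mean and not replace it.
- **Defining a missed block could set when a second attempt begins.** Any definition should therefore serve the analysis only.

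A reader might also infer more than the documents support:

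- **That recorded scores are deleted.** The documents do not say so; they say the child is excluded and are silent on the data.
- **That calling the event a confounder contradicts the exclusion.** It reads more naturally as the reason for it.
- **That pain is estimated with bias, or that buffering's onset benefit is understated by some percentage.** The first has not been shown. The second would rest on an assumed onset model and assumed miss rates.

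**Conclusion.** The point holds in limited form. A result seen after assignment and after pain scoring removes the child, and nothing in 5.5.1 restores the data.

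For pain, the harm is lost pairs: 1.3–4.4 complete pairs of 55 before other attrition, if half the children receive IANB and 5–20% of injections miss. The power difference is about 1 to 3 points, and power falls below the planned 90% only if misses come on top of the 20% attrition. A larger IANB share widens the difference.

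For onset, the IANB comparison is conditional on block success. The mean in seconds can be biased only if the solution affects that success, and no size can be given. This does not describe infiltration children, for whom the gap is the absence of any rule.

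The change is worth making because it is cheap and settles which children are analysed, not because the trial would otherwise fail.

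**What to change.** Changes to the analysis only:

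(a) **Pain.** Reword 5.1, criterion 8 and 5.5.1 so that a missed block does not remove pain scores already recorded. Analyse every child with pain scores at both visits, and give the analysis without missed blocks as a sensitivity analysis.

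(b) **Failures.** Record block or infiltration failure (yes/no) at each visit. Report failures by solution, overall and at visit 1, where the coin flip gives a comparison not yet affected by exclusions.

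(c) **Onset.** State that the paired mean in seconds applies only to pairs in which anesthesia was reached at both visits. Add a sensitivity analysis, for both techniques, that keeps unreached onset as the worst value in a paired rank test; a pair not reached at either visit is a tie. Define not reached for the analysis alone.

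The cost is wording, one extra recorded item per visit and one extra onset analysis, which does not itself give a result in seconds. When a second attempt is made, and whether a child continues to visit 2, remain clinical decisions for the sponsor. If children stop after a visit-1 miss, only visit-2 misses are recovered.
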